### Appendix 3. Blood Pressure Levels for Girls and Boys by Age

The following tables were taken from “The Fourth Report on the Diagnosis, Evaluation, and Treatment of High Blood Pressure in Children and Adolescents” PEDIATRICS Vol. 114 No. 2 August 2004, pp. 555-576.

Instructions for using these BP Charts:

1. Measure the patient’s BP using an appropriate size cuff.
2. Select appropriate chart for a female or male patient.
3. Using the “age” row and “height” column, determine if the BP is within the ULN. The BP tables use height percentile data found on the CDC growth charts ([www.cdc.gov/growthcharts](http://www.cdc.gov/growthcharts)). See below.
4. See [Section 5.2.11](#) for suggested guidelines for medical treatment of sunitinib-related hypertension.

#### Blood pressure (BP) levels for GIRLS aged 6-17 years

Age Years	BP Percentile	Systolic Blood Pressure, mm Hg							Diastolic Blood Pressure, mm Hg						
		Percentage of Height							Percentage of Height						
		5th	10th	25 th	50th	75th	90th	95th	5th	10th	25th	50th	75th	90th	95th
6	95th	108	109	110	111	112	113	114	72	72	73	74	74	75	76
7	95th	110	111	112	113	115	116	116	73	74	74	75	76	76	77
8	95th	112	112	114	115	116	118	118	75	75	75	76	77	78	78
9	95th	114	114	115	117	118	119	120	76	76	76	77	78	79	79
10	95th	116	116	117	119	120	121	122	77	77	77	78	79	80	80
11	95th	118	118	119	121	122	123	124	78	78	78	79	80	81	81
12	95th	119	120	121	123	124	125	126	79	79	79	80	81	82	82
13	95th	121	122	123	124	126	127	128	80	80	80	81	82	83	83
14	95th	123	123	125	126	127	129	129	81	81	81	82	83	84	84
15	95th	124	125	126	127	129	130	131	82	82	82	83	84	85	85
16	95th	125	126	127	128	129	130	131	82	82	82	83	85	85	86
≥17	95th	125	126	127	129	130	131	132	82	83	83	84	85	85	86

**Blood pressure (BP) levels for BOYS aged 6-17 years**

Age	BP	Systolic Blood Pressure, mm Hg							Diastolic Blood Pressure, mm Hg						
		Percentage of Height							Percentage of Height						
Years	Percentile	5th	10th	25 th	50th	75th	90th	95th	5th	10th	25th	50th	75th	90th	95th
6	95th	109	110	112	114	115	117	117	72	72	73	74	75	76	76
7	95th	110	111	113	115	117	118	119	74	74	75	76	77	78	78
8	95th	111	112	114	116	118	119	120	75	76	77	78	79	79	80
9	95th	113	114	116	118	119	121	121	76	77	78	79	80	81	81
10	95th	115	116	117	119	121	122	123	77	78	79	80	81	81	82
11	95th	117	118	119	121	123	124	125	78	78	79	80	81	82	82
12	95th	119	120	122	123	125	127	127	78	79	80	81	82	82	83
13	95th	121	122	124	126	128	129	130	79	79	80	81	82	83	83
14	95th	124	125	127	128	130	132	132	80	80	81	82	83	84	84
15	95th	126	127	129	131	133	134	135	81	81	82	83	84	85	85
16	95th	129	130	132	134	135	137	137	82	83	83	84	85	86	87
≥17	95th	131	132	134	136	138	139	140	84	85	86	87	87	88	89

#### **Appendix 4. Response Evaluation Criteria in Solid Tumors (RECIST) Version 1.1.**

Adapted from Eisenhauer et al (2009) Eur 2009 Jan;45(2):228-47.

##### **a. Measurability of Lesions**

*Measurable disease.*

1. Lesions with longest diameter 10 mm or greater in the axial plane (bone lesions not included except for soft tissue expansile masses arising from bone) when assessed by MRI or CT.
2. Lesions with longest diameter at least 20 mm when assessed by X-ray.
3. Superficial lesions with longest diameter 10 mm or greater when assessed by caliper.
4. Malignant lymph nodes with the short axis 15 mm or greater when assessed by MRI or CT.

A previously irradiated lesion is not measurable unless it has progressed since completion of RT.

MRI and CT should be performed with cuts of 5 mm or less in slice thickness contiguously. If greater than 5 mm, then minimum lesion size should be twice the slice thickness.

*Non-measurable disease.*

All other lesions including lesions too small to be considered measurable, pleural or pericardial effusions, ascites, bone disease, inflammatory breast disease, leptomeningeal disease, lymphangitis, pulmonitis, clinical lesions that cannot be accurately measured with calipers, abdominal masses identified by physical exam that are not measurable by reproducible imaging techniques, nodes with short axis  $\geq 10$  but  $< 15$  mm, disease documented by indirect evidence only (eg, by lab values), or previously radiated lesions that have not progressed.

*Target and non-target disease.*

Target lesions. All measurable lesions up to a maximum of 2 lesions per organ, 5 lesions in total, representative of all involved organs, should be identified as target lesions at baseline. Target lesions should be selected on the basis of size (longest lesions) and suitability for accurate repeated measurements. Measurements must be provided for target measurable lesions.

Non-target disease: All non-measurable disease is non-target. All measurable lesions not identified as target lesions are also included as non-target disease.

All sites of disease must be assessed at baseline. Baseline assessments should be done as close as possible prior to study start. For an adequate baseline assessment, all required scans must be done within 4 weeks prior to treatment and all disease must be documented appropriately. If baseline assessment is inadequate, subsequent statuses generally should be indeterminate. Note: A tumor is considered evaluable but not measurable if an increase in tumor mass can be assessed even though it does not meet the minimum requirements for measurability as defined by RECIST v1.1. Examples would include ascites, pericardial effusion, or pleural effusion.

Objective Status is to be recorded at each evaluation.

Disease sites must be assessed using the same technique as baseline, including consistent administration of contrast and timing of scanning. If a change needs to be made the case must be discussed with the radiologist to determine if substitution is possible. If not, subsequent objective statuses are indeterminate.

Complete Response (CR): Complete disappearance of all target and non-target disease, with the exception of nodal disease. All nodes, both target and non-target, must decrease to normal size (short axis <10 mm). No new lesions. All disease sites must be assessed.

Partial Response (PR): Applies only to patients with at least one measurable lesion. Greater than or equal to 30% decrease under baseline of the sum of diameters of all target measurable lesions. The short diameter is used in the sum for target nodes, while the longest diameter is used in the sum for all other target lesions. No unequivocal progression of non-target disease. No new lesions. No reappearance of lesions after a CR. All target lesions must be assessed.

Stable: Does not qualify for CR, PR, Progression. All target lesions must be assessed.

Objective Progression: One or more of the following must occur. 1) 20% increase in the sum of diameters of target measurable lesions above the smallest sum observed (over baseline if no decrease in the sum is observed during therapy), with a minimum absolute increase of 5 mm. The short diameter is used in the sum for target nodes, while the longest diameter is used in the sum for all other target lesions. 2) Unequivocal progression of non-target disease. Unequivocal progression is assessed with respect to non-target disease as a whole, not to each individual lesion. An explanation must be provided. 3) Appearance of any new lesion/site. 4) Reappearance of lesions after a CR. 5) A modest increase in an evaluable but not measurable tumor is usually not considered sufficient to indicate unequivocal disease progression.

Indeterminate, objective status unknown. Progression has not been documented, and

- One or more target measurable lesions have not been assessed;
- Or assessment methods used were not the same as baseline;

- Or one or more target lesions cannot be measured accurately unless due to being too small to measure;
- Or one or more target lesions were excised or irradiated and have not reappeared or increased.

Objective status notes:

- Non-target disease does not necessarily affect objective status except in determination of CR (must be absent--a patient who otherwise has a CR, but who has non-measurable or non-target measurable disease present or not assessed, can at best be classified as PR), and in determination of progression (if new lesions develop or if unequivocal progression occurs). Cases for which target disease is assessed as stable or better but non-target assessments are missing must be reviewed carefully. By considering the whole sequence, it may be reasonable to assume missed non-target assessments were not progression;
- For unequivocal progression of non-target disease, generally the overall tumor burden must increase sufficiently to merit discontinuation of therapy. In the presence of SD or PR in target disease, progression due to unequivocal increase in non-target disease should be rare. In particular, increase of a single small non-target measurable lesion by 20% would not ordinarily constitute unequivocal increase in non-target disease as a whole;
- An objective status of PR or stable cannot follow one of CR. Stable can follow PR only in the rare case that tumor increases by less than 20% from the nadir, but enough that a previously documented 30% decrease no longer holds;
- For bone disease documented on bone scan only, increased uptake does not constitute unequivocal progression;
- Appearance or worsening of pleural effusions does not constitute unequivocal progression unless cytologically proven of neoplastic origin. In the case of worsening, the change must be substantial, eg, from trace to large;
- If CR determination depends on a residual lesion that decreased in size but did not disappear completely, it is recommended the residual lesion be investigated with biopsy or fine needle aspirate;
- If progression determination depends on a lesion with an increase possibly due to necrosis, the lesion may be investigated with biopsy or fine needle aspirate to clarify status;
- If two target lesions coalesce the measurement of the coalesced mass is used. If a large target lesion splits, the sum of the parts is used;

- Measurements for target lesions that become small should continue to be recorded. If a target lesion becomes too small to measure, 0 mm should be recorded if the lesion is considered to have disappeared; otherwise a default value of 5 mm is used;
- If a new lesion is identified in a location not scanned at baseline, this is considered progression;
- PET results are not used in determination of objective status;
- Disease that is poorly visible on scan such that status or size cannot be adequately determined should be assessed as Indeterminate;
- If a target lesion becomes non-evaluable (for reasons other than too small) this is recorded as indeterminate;
- Measurable lesions that are irradiated or excised on study are no longer measurable and should be assessed as Indeterminate on the Tumor Assessment-Target Lesions CRF. Subsequent increase or reappearance may constitute progression of disease.

## Appendix 5. Lansky and ECOG Performance Scales

Lansky Scale to be used for patients aged <11 years. ECOG Scale to be used for patients aged ≥11 years.

Score	Lansky	Score	ECOG
100%	Fully active	0	Normal, no complaints
90%	Minor restriction in physically strenuous play	1	Mild complaints for physical activities, but patient needs no assistance and can do easy work
80%	Restricted in strenuous activities, tires more easily, otherwise active		
70%	Both greater restriction of, and less time spent in active play	2	Ambulatory, patient cares for self, but age-appropriate activity severely impaired
60%	Ambulatory up to 50% of time, limited active play with assistance/supervision		
50%	Frequently nursing in bed during day, considerable assistance required for any active play, fully able to engage in quiet play	3	Confined to bed more than 50% of time, needs nursing care
40%	Frequently confined to bed; able to initiate quiet activities		
30%	Confined to bed, needs assistance for quiet activities	4	Confined to bed or prostrated on chair, needs intensive care
20%	Frequently asleep, limited to very passive activity initiated by others		
10%	Completely disabled, not even passive play		
0%	No reaction		

Adapted from J Clin Onc, 2003. 21(22): p. 4235-4238.

## Appendix 6. Sunitinib Total Daily Dose Levels per BSA

Pediatric doses are stated in mg (rounded to a multiple of 6.25 mg), based on individual patient BSA (m^2) at daily dose levels of 15 mg/m^2, 22.5 mg/m^2 or 30 mg/m^2 never exceeding 50 mg/day.

Dose Level (mg/m^2)	BSA (m^2)	Total Dose (mg)
15	≤0.62	6.25
	0.63-1.03	12.50
	1.04-1.45	18.75
	1.46-1.87	25.00
	1.88-2.28	31.25
	2.29-2.70	37.50
	2.71-3.12	43.75
	3.13-3.53	50.00
<hr/>		
22.5	≤0.41	6.25
	0.42-0.68	12.50
	0.69-0.96	18.75
	0.97-1.24	25.00
	1.25-1.52	31.25
	1.53-1.80	37.50
	1.81-2.07	43.75
	≥2.08	50.00
<hr/>		
30	≤0.30	6.25
	0.31-0.51	12.50
	0.52-0.72	18.75
	0.73-0.93	25.00
	0.94-1.14	31.25
	1.15-1.34	37.50
	1.35-1.55	43.75
	1.56-1.76	50.00
<hr/>		
≥1.77	50.00	≥1.77	50.00

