#### **5.2.5. For Children (age less than 18 years at enrollment)**

Dosing for all cycles will be based on the BSA obtained at the start of each cycle.

BSA for dosing should be calculated using the Mosteller formula.

$$\text{BSA in m}^2 = [(\text{height in cm} \times \text{weight in kg})/3600]^{1/2}$$

<http://www.halls.md/body-surface-area/bsa.htm>

The sunitinib intended starting dose will be 15 mg/m^2/day (not to exceed 50 mg/day) on Schedule 4/2. (See [Appendix 6](#)).

Intra-patient dose escalation of sunitinib will be allowed after completion of Cycle 1 based on dose modification guidelines detailed in [Section 5.2.8](#). Dose escalation will be in increments of 7.5 mg/m^2, up to a maximum dose of 30 mg/m^2 (not to exceed 50 mg/day). The dose and the dose change increments will be rounded to the nearest number which is a multiple of 6.25 mg, the lowest dose strength available. After Cycle 1, when the minimum frequency of clinic visits is reduced, an additional Day 15 visit is required if the sunitinib dose is escalated during that cycle.

At each dose level (mg/m^2), based on each individual patient body surface area (BSA) the calculated total dose in mg is rounded to the nearest number which is a multiple of 6.25 mg, the lowest dose strength available (See [Table 5](#) for the available doses). The rounded doses considering an individual patient's BSA for daily Dose Levels of 15 mg/m^2, 22.5 mg/m^2 and 30 mg/m^2 have been provided in [Appendix 6](#).

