### 5.2.8. Dose Modifications

Patients will be monitored for toxicity, and the sunitinib dose may be adjusted according to individual patient tolerance at the discretion of the investigator. The available doses were presented in [Table 5](#) above. After Cycle 3, when the frequency of clinic visits may be reduced to a minimum of once per cycle, investigators may wish to include more frequent visits for assessment of blood pressure and/or to perform clinically indicated laboratory tests if sunitinib related toxicities are expected or observed. The following are suggested guidelines that investigators may use as a reference.

For patients  $<18$  yrs, intra-patient dose escalation of sunitinib will be allowed after completion of Cycle 1 and/or later cycles, and in the absence of toxicity greater than Grade 1 in the prior cycle, with exceptions listed in the footnotes to [Table 6](#). Dose escalation will be in increments of  $7.5 \text{ mg/m}^2$ , up to a maximum dose of  $30 \text{ mg/m}^2$  (not to exceed  $50 \text{ mg/day}$ ). The sunitinib dose may be reduced in response to toxicities based on investigator discretion, with general guidelines listed in [Table 6](#). Dose reductions in patients  $<18$  yrs will be in decrements of  $7.5 \text{ mg/m}^2$ . For young adults aged  $18- < 21$  years, inclusive, the intra-patient dose modification will be in  $12.5 \text{ mg}$  increments or decrements, consistent with Sutent® drug label recommendation.

Sunitinib will be held for Grade 3 and 4 toxicities until the toxicity decreases to Grade 1 ( $\leq$ Grade 2 for hematologic toxicities) or baseline, at which point sunitinib will be resumed as detailed in [Table 6](#) below. Re-escalation will be permitted with appropriate supportive care and monitoring at the discretion of the investigator.

Recurrence of Grade 3 or greater toxicity will require dose reduction until toxicity has resolved to baseline.

Any patient requiring >4 weeks of dose interruption for toxicity should be considered for study withdrawal.

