**Table 6. Dose Modifications for Toxicity Attributed to Sunitinib for Patients <18 Years of Age**

Toxicity	Grade 0-1	Grade 2	Grade 3	Grade 4
Non-hematologic 	May escalate 1 dose level  or, if escalation previously attempted and reversed, continue at the same dose level.	Continue at the same dose level.	Withhold dose until toxicity is grade $\leq 1$ or has returned to baseline, then resume treatment at the same dose level (assuming non-recurrent) or reduce the dose by 1 level at the discretion of the investigator. 	Withhold dose until toxicity is grade $\leq 1$ or has returned to baseline, then reduce the dose by 1 level and resume treatment, or discontinue at the discretion of the investigator. 
Hematologic	May escalate 1 dose level or, if escalation previously attempted and reversed, continue at the same dose level.	Continue at the same dose level.	Withhold dose until toxicity is grade $\leq 2$ or has returned to baseline, then resume treatment at the same dose level or reduce the dose by 1 level at the discretion of the investigator. 	Withhold dose until toxicity is grade $\leq 2$ or has returned to baseline, then reduce the dose by 1 level and resume treatment. 

1. A dose level will be considered 7.5 mg/m^2 increase or decrease from current dose.
3. Patients who develop Grade 4 hyperuricemia or Grade 3 hypophosphatemia without clinical symptoms may continue study treatment without interruption at the discretion of the investigator. Nausea, vomiting and/or diarrhea should persist at Grade 3 or 4 despite maximal medical therapy before reducing the sunitinib dose.
4. Patients who develop Grade 3 or 4 lymphopenia may continue study treatment without interruption.
5. For hypertension guidelines reference [Section 5.2.11](#).

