### **5.2.9. Minimum Sunitinib Dose Allowed**

#### **For Children**

Pediatric patients already receiving an absolute dose of 6.25 mg at the time of an indicated dose reduction must be removed from protocol therapy.

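### The pediatric dose-reduction passages disagree: a one-level step from a capped 50 mg dose can be 0 mg or up to 18.75 mg, and the 6.25 mg removal rule does not fit the 7.5 mg/m² steps below the starting dose

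*Protocol*

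**What the plan says.** All of this is in the Protocol.

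- **Start (Section 5.2.5).** "The sunitinib intended starting dose will be 15 mg/m 2 /day (not to exceed 50 mg/day) on Schedule 4/2".
- **Rounding (Section 5.2.5).** At each level, "the calculated total dose in mg is rounded to the nearest number which is a multiple of 6.25 mg", and the rounded doses are referred to Appendix 6. The same section also says: "The dose and the dose change increments will be rounded to the nearest number which is a multiple of 6.25 mg".
- **Size of a step.** Section 5.2.8 sets pediatric reductions in decrements of 7.5 mg/m². Footnote 1 of Table 6 says: "A dose level will be considered 7.5 mg/m 2 increase or decrease from current dose".
- **Reduction after Grade 4 non-hematologic toxicity (Table 6).** Withhold, "then reduce the dose by 1 level and resume treatment, or discontinue at the discretion of the investigator".
- **Tabulated doses (Appendix 6).** Rows exist "at daily dose levels of 15 mg/m 2 , 22.5 mg/m 2 or 30 mg/m 2 never exceeding 50 mg/day". There is no 7.5 mg/m² block. The 22.5 mg/m² block ends with 50 mg at BSA 2.08 m² or more. The 30 mg/m² block gives 50 mg from 1.56 m² upward.
- **Floor (Section 5.2.9).** "Pediatric patients already receiving an absolute dose of 6.25 mg at the time of an indicated dose reduction must be removed from protocol therapy".

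Section 5.2.8 presents the modification rules as suggested guidelines for reference. It also makes a dose reduction a requirement when Grade 3 or worse toxicity recurs.

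**The concern.** A site that has to lower a child's dose needs one answer in mg. At the top of the range, the table and the footnote give different answers, and the table's answer can be no change at all. At the bottom, the step rule runs out at 0 mg/m² while the removal rule waits for an absolute dose that some children never pass through. Whether such a child stops or continues then depends on which section the site follows.

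The analysis is affected too. A secondary objective is whether doses above the pediatric MTD are tolerated. If dose level is recorded by its nominal label, a 50 to 50 mg step can be counted as an escalation or a reduction, and a capped dose can be reported as 30 mg/m². With six children, one misclassification is 1/6, or about 17% of the pediatric cohort.

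**Working it through.** **Readings of one level down.** The text allows three.

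- A: step the nominal mg/m² level, multiply by BSA, round to the nearest 6.25 mg (Section 5.2.5 and Appendix 6).
- B: subtract 7.5 × BSA from the mg dose delivered, then round (Table 6, footnote 1).
- C: round 7.5 × BSA to a multiple of 6.25 mg, then subtract it from the mg dose delivered (the Section 5.2.5 sentence on increments).

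**Reproducing Appendix 6.** At 22.5 mg/m² the change from 43.75 to 50 mg falls at their midpoint: 46.875 / 22.5 = 2.0833 m². The table shows 2.08. Strictly, 22.5 × 2.08 = 46.8 mg lies nearer 43.75, so the rounding rule alone gives 50 mg from 2.09. Other rows show the same 0.01 m² effect, and apart from it reading A reproduces the table. Reading C, applied upward over BSA 0.60–2.07 m², disagrees with the table at 27 of 148 values for 15 to 22.5 mg/m² and at 30 of 148 for 22.5 to 30 mg/m².

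**Top end: one level down from a nominal 30 mg/m² (50 mg).**

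| BSA (m²) | Appendix 6 (A) | Footnote 1 (B) |
|---|---|---|
| 1.81 | 43.75 mg | 50 − 13.575 = 36.425, rounds to 37.5 mg |
| 2.07 | 43.75 mg | 50 − 15.525 = 34.475, rounds to 37.5 mg |
| 2.08 | 50 mg | 50 − 15.6 = 34.4, rounds to 37.5 mg |
| 2.10 | 50 mg | 50 − 15.75 = 34.25, rounds to 31.25 mg |

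Reading C gives the same doses as B in these four rows. As a fraction of 50 mg, the reductions are 12.5% against 25% at 1.81–2.07 m², 0% against 25% at 2.08, and 0% against 37.5% at 2.10. The move up from 22.5 to 30 mg/m² is also 50 to 50 mg from 2.08 m². There the dose is at most 50 / 2.08 = 24.0 mg/m².

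**Low end: successive steps from the 15 mg/m² start.** In nominal terms, 15 − 7.5 − 7.5 = 0 mg/m² at every BSA. The 7.5 mg/m² level changes from 6.25 to 12.5 mg at 9.375 / 7.5 = 1.25 m². That value is an exact tie and no tie rule is stated, so the statements below concern BSA above 1.25 m².

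| BSA (m²) | A | B and C | 6.25 mg reached? |
|---|---|---|---|
| 1.26–1.45 | 18.75, 12.5, 0 | 18.75, 6.25 | B and C only |
| 1.46–1.87 | 25, 12.5, 0 | 25, 12.5, 0 | none |
| 1.88–2.08 | 31.25, 12.5, 0 | 31.25, 18.75, 6.25 | B and C only |
| 2.09–2.28 | 31.25, 18.75, 0 | 31.25, 12.5, then below 0 | none |

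Worked case at 1.73 m², the BSA that Section 1.3.6 uses to convert adult doses. The start is 15 × 1.73 = 25.95, rounded to 25 mg. One step is 7.5 × 1.73 = 12.975 mg. A gives 12.975, rounded to 12.5 mg. B gives 25 − 12.975 = 12.025, also rounded to 12.5 mg. C gives 25 − 12.5 = 12.5 mg. The next step is 0 mg under A and C, and under B it is 12.5 − 12.975 = −0.475, which rounds to 0. The removal rule is not met on any of them.

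**The case against.** **The rules are advisory.** Section 5.2.8 offers guidelines and investigator discretion, Table 6 allows discontinuation for Grade 4 non-hematologic toxicity, and Section 6.4 allows withdrawal for unacceptable toxicity. So no child is bound to stay on 50 mg after a toxicity, and a reader who inferred that would go beyond the text. But Section 5.2.8 does require reduction for recurrent Grade 3 or worse toxicity, Section 5.2.9 is mandatory, and discretion does not say which passage governs.

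**The top-end result depends on the level a capped child is deemed to hold.** A child of 2.08 m² or more is already on 50 mg at 22.5 mg/m². If that child is treated as still at 22.5, one level down is the 15 mg/m² row: 31.25 mg for BSA 1.88–2.28 m². From 2.09 to 2.28 m² that equals the footnote 1 result. This stands, but the text does not say which level applies.

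**The low-end gap is narrower than it may seem.** A reader might infer that every child above 1.25 m² falls into it, or that it concerns most adolescents needing two reductions. The first holds only on the nominal-level reading. A child of 150 cm and 40 kg (Mosteller BSA √(150 × 40 / 3600) = 1.29 m²) reaches 6.25 mg on reading B: 18.75 − 9.675 = 9.075, rounded to 6.25. The second has no BSA data behind it. It is also fair that a step to 0 mg/m² can be read as stopping the drug, and that Section 5.2.9 does not promise that every child passes through 6.25 mg. Still, the protocol does not say so.

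**The effect on results is limited.** A capped dose of about 24 mg/m² still exceeds the 15 mg/m² MTD, so the secondary objective is not defeated, and no endpoint is defined as tolerance at 30 mg/m². Dosing data are collected, and SAP Section 9.1.4 summarizes dose adjustments. The remaining risk is one of labeling.

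**Conclusion.** The passages conflict and need reconciling. At BSA of 2.08 m² or more, one level down from a nominal 30 mg/m² is 0 mg by Appendix 6, and 12.5 mg (at 2.08) or 18.75 mg (at 2.10) by footnote 1. At 1.81–2.07 m² it is 6.25 mg against 12.5 mg. These differences assume that the capped child is held at the 30 mg/m² level.

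At the low end, the firmest result is for BSA 1.46–1.87 m²: all three readings give 25, 12.5, 0 mg and none meets the 6.25 mg rule. Whether the rule is met at 1.26–1.45 and 1.88–2.08 m² depends on the reading. At 2.09–2.28 m² no reading meets it, but the first-step dose differs (18.75 or 12.5 mg). The low-end doses are derived from the rounding rule, because Appendix 6 has no 7.5 mg/m² rows.

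How many children are affected cannot be estimated, since no BSA distribution is given. Six children were already enrolled at Amendment 2 and further enrollment was thought unlikely, so the prospective effect is limited. The classification issue applies to their data in any case, if any of them reached a capped dose.

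**What to change.** The sponsor should reconcile Appendix 6, Table 6 footnote 1 and Sections 5.2.5, 5.2.8 and 5.2.9 so that they give the same result in each BSA band. Three points need stating:

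1. whether a level is counted from the nominal mg/m² level or from the dose delivered;
2. which level a child capped at 50 mg holds;
3. how the step below 7.5 mg/m² relates to the 6.25 mg removal rule.

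The doses and the rules are for the sponsor to decide; none is proposed here.

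In the SAP, classify dose and tolerability by the mg and mg/m² actually given. A capped 50 mg dose at BSA of 2.08 m² or more should not be reported as 30 mg/m², and a 50 to 50 mg step should count as neither an escalation nor a reduction.

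The cost is a few table rows, a sentence or so in each of the sections concerned and one derivation rule in the SAP. It should need no new data or visits: dosing information is already collected, and height and weight are recorded on Day 1 of each cycle for children.
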